## **5.9 Injection Visit Windows**

The visit windows for all visits, including injection visits, are outlined in the SSP Manual. Refer to SSP for instruction on managing participants who report to clinic outside of injection window.

The target visit windows for all visits, including injection visits, are outlined in the SSP Manual. In brief, the target visit window for all injection visits is +/- 3 days. Visits conducted outside of the target visit windows are allowable without restriction and are also defined in the SSP Manual for scheduling guidance. Each study visit, including the injection visit, should ideally be conducted within the target date range. When that is not possible, visits outside of the target dates may be completed.

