## 12.3 APPENDIX III. SCHEDULE OF EVALUATIONS –FOLLOW-UP PHASE (STEP 3-ORAL PrEP)

WEEKS SINCE LAST INJECTION	Wk +8	Wk +12	Wk +24	Wk +36	Wk +48	Early Discontinuation
ADMINISTRATIVE, BEHAVIORAL, REGULATORY						
Locator information	X	X	X	X	X	X
HIV prevention & risk reduction counseling	X	X	X	X	X	X
Condoms per local SOC	X	X	X	X	X	X
Behavioral/Acceptability assessment (CASI)		X	X	X	X	X
CLINICAL EVALUATIONS & PROCEDURES						
Qualitative interviews continue (approximately)		X	X			
Medical history  , concomitant medications, targeted physical exam		X	X	X	X	
Hep B vaccination (if needed) 						X
Blood collection	X	X	X	X	X	
Urine collection			X		X	X
Rectal swab collection			X		X	
Provision of Tenofovir/Emtricitabine (Trade name: TDF/FTC, Truvada®) (3 months' worth)		X	X	X		X
LOCAL LABORATORY EVALUATIONS & PROCEDURES						
HIV testing 		X	X	X	X	
CBC with differential			X		X	X
Chemistry testing 		X	X	X	X	X
Liver function testing 		X	X	X	X	X
Syphilis testing			X			X
GC/CT testing (urine, rectal, and oral pharyngeal swabs)			X		X	
Urinalysis (protein, glucose; at the clinic or local lab)			X		X	X
Plasma storage 	X	X	X	X	X	
DBS storage		X	X		X	
HBsAb and HBcAb 					X	X
HCVAb					X	X

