2.1 General Design Considerations

HPTN083-01 is a phase IIB single arm trial designed to establish the minimum safety, tolerability and acceptability data needed to support the use of cabotegravir long-acting injection (CAB LA) in an adolescent population, potentially transforming the field of HIV prevention for young people. The study target population is sexually active, healthy male adolescents aged below 18 years. The study target is to enroll more than 50 participants with at least 50 participants receiving at least one injection. Participant recruitment will take approximately 12 months.

Study participation includes Step 1: a 5-week oral CAB 30mg QD safety lead-in followed by Step 2: a series of 5 intramuscular (IM) injections of 3 mL (600 mg) cabotegravir administered at 8-week intervals after a 4-week loading dose (injections at weeks 5, 9, 17, 25 & 33). Adherence support strategies (e.g., counseling, reminders, pill cases) will be included to support pill-taking during the first five weeks and to support retention during the injectable phase. A safety visit will follow each injection to ascertain pharmacokinetic-peak safety data, including injection site reactions. Step 3: A blood draw visit, the +8 Week Visit, will follow the week 33 injection to monitor CAB drug levels. All participants who have received at least one injection will be followed for 48 weeks after their last injection. Waning levels of cabotegravir (the PK tail) will be covered with locally sourced oral TENOFOVIR/EMTRICITABINE (TRADE NAME: TDF/FTC, TRUVADA®) for daily use for 48 weeks. In Step 3 participants may also choose to continue with 8-week dosing of injectable of CAB-LA for 48 weeks (5 additional injections beyond the initial 5 injections, administered at weeks +8, +16, 24, +32, +40, and +48.) Behavioral and acceptability data will be collected via computer-assisted self-interview (CASI). Total participant commitment for the entire study is up to 87 weeks, or approximately 1.5 years. We anticipate recruitment for the study will take approximately 12 months.

Participants who discontinue study product during Step 2 for any reason other than HIV infection or AE occurrence will be transitioned to open label TDF-FTC for 48 weeks.

There are in total three study sites:

- Adolescent and Young Adult Research at the Core Center (AYAR at CORE), Chicago, IL;
- St. Jude Children's Research Hospital CRS, Memphis, TN;
- Fenway Health CRS, Boston, MA.

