8.1 Safety endpoint analysis

Cohort: Injection population

Analysis description: Number and percent of participants experiencing any Grade 2 or higher clinical adverse events (AEs) or laboratory abnormalities (reported as adverse events) from the first injection visit to 8 weeks after the last Step 2 injection visit, or Week 41, whichever comes first. See Section 3.2 for details regarding aggregation and tabulation of AEs.

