12.1 Plasma CAB pharmacokinetics

Analysis details are provided in the current version of the Pharmacokinetics Analysis Plan

12.2 Proportion of participants experiencing Grade 2 or higher clinical AEs and laboratory abnormalities in the oral phase and over the entire study period

Cohort: Safety population

Analysis description: Number and percent of participants experiencing any Grade 2 or higher clinical adverse events (AEs) or laboratory abnormalities from:

1. enrollment to week 5 (oral phase (step 1), including interim visits).
2. enrollment to 8 weeks following the last injection received (aggregate over oral+injection phases (step 1-step 2) including interim visits)

12.3 Proportion of participants receiving one or more injections who experience Grade 2 or higher clinical AEs and laboratory abnormalities from initial injection to 36 weeks later

Population: Injection population

Analysis description: Number and percent of participants experiencing any Grade 2 or higher clinical adverse events (AEs) or laboratory abnormalities from the first injection visit to approximately 36 weeks later regardless of whether participants received all 5 injections. For participants receiving all 5 injections, the end date is 8 weeks following the week 33 injection visit. For participants discontinuing study product early and moving on to Step 3, the end date is 36 weeks after the initial injection. Participants who terminate early are included in the analysis and censored at the date of termination.

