12.4 Proportion of injection visits that occurred “on-time”

Population: Injection population

Analysis description: Number and percent of injection visits (up to 5 per participant) that occur “on-time”¹, using the number of injections given as the denominator. This will be presented along with the total number and percent of injections given, among all intended injections (i.e. 5 injections per participant).

¹The target injection date is defined by the W5 visit i.e. for the initial injection, the target injection date is 0 days (same day), and is +28, +84, +140, +196 days from the W5 visit for injections 2-5, respectively. The target visit window for injection visits for the week 5 injection is 0 to 3 days after the W5 visit (if the injection could not be done on the same day as the W5 visit), for all other injection visits (W9, W17, W25, W33) the target window is +/-3 days from the target injection date. Injection dates happening within the target window are considered “on-time”.

12.5 Change from enrollment of self-reported sexual behavior (number of sexual partners, and number of episodes of anal intercourse without a condom) during the study period

Note: This secondary analysis will not be included in the Clinical Study Report.

Population: Enrolled population

Analysis description: Counts of sexual partners and episodes of anal intercourse without a condom will be summarized (mean and median) at enrollment and each regular Step 1 and Step 2 follow-up visit (W4, W5, W9, W17, W25, W33, +8).

12.6 Evaluate rates of HIV drug resistance among participants who acquire HIV infection during the study

Population: Seroconverter population

Analysis description: Data from steps 1, 2, and 3 will be included. The number of cases of drug resistance will be summarized. All cases of drug resistance among incident HIV infections will be described.

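### The Week 41 cap in SAP 8.1 shortens primary safety follow-up when the last Step 2 injection is late, which the uncapped windows in SAP 12.2 and 12.3 do not

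*SAP*

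**What the plan says.** SAP 8.1 defines the primary safety window for the injection population as running "from the first injection visit to 8 weeks after the last Step 2 injection visit, or Week 41, whichever comes first". It gives no anchor for Week 41. The Step 3 schedules in Protocol Appendices III and IV contain no visit of that name; their columns are headed "WEEKS SINCE LAST INJECTION" and begin at +8.

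SAP 2.1 plans "injections at weeks 5, 9, 17, 25 & 33". SAP 12.4 fixes the targets at "28, +84, +140, +196 days from the W5 visit for injections 2-5" and, for injections 2 to 5, says "the target window is +/-3 days from the target injection date". Late injections are foreseen. Protocol 5.9 states that "Visits conducted outside of the target visit windows are allowable without restriction" and refers to the SSP Manual for details. SAP 12.4 makes timeliness a secondary endpoint: "Number and percent of injection visits (up to 5 per participant) that occur “on-time".

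Two secondary safety windows have no Week 41 limit. SAP 12.2, item 2, runs from enrollment to 8 weeks after the last injection received. SAP 12.3 says: "For participants receiving all 5 injections, the end date is 8 weeks following the week 33 injection visit". Protocol 7.7.1 sets the primary window longer than any of these, to 48 weeks after the last injection.

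**The concern.** The two limits in SAP 8.1 coincide for a participant whose fifth injection is on its target day. For someone who stops early, the 8-week limit normally ends the window. The Week 41 limit therefore has an effect only when the last Step 2 injection is late, and that effect can only be to take away time after the injection. No reason is given for it.

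The primary objective includes the safety of CAB LA. For a late completer, a Grade 2 or higher event that begins after Week 41 but within 8 weeks of the fifth injection would count in SAP 12.3 and in SAP 12.2, item 2, but not in SAP 8.1. The primary analysis would then be narrower than the secondary ones for the same person, always in the direction of fewer events. The missing anchor adds a programming risk: counted from enrollment instead of from the W5 visit, Week 41 would also cut follow-up for a participant whose W5 visit was late, even with every injection on time by the SAP 12.4 definition.

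**Working it through.** **1. Reproduce Week 41.** From the schedule, 33 + 8 = 41. From the SAP 12.4 targets, injection 5 is due at day 196 after the W5 visit, and 196 + 56 = 252 days = 36 weeks; 5 + 36 = 41. This agrees with the approximately 36 weeks in SAP 12.3.

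**2. When the cap binds.** Let d be the delay of injection 5 in days, with Week 41 taken as day 252 from the W5 visit. The 8-week limit falls at 196 + d + 56 = 252 + d. The window ends at min(252 + d, 252). For d ≤ 0 the cap does nothing (at d = −3 the window ends at day 249 with or without it). For d > 0 it ends at 252.

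**3. Follow-up kept after injection 5** = max(0, 56 − d).

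| Delay d (days) | End without cap (day) | End under SAP 8.1 (day) | Days kept | Days lost |
|---|---|---|---|---|
| 0 | 252 | 252 | 56 | 0 |
| 3 (still on time) | 255 | 252 | 53 | 3 (5.4%) |
| 7 | 259 | 252 | 49 | 7 (12.5%) |
| 14 | 266 | 252 | 42 | 14 (25%) |
| 28 | 280 | 252 | 28 | 28 (50%) |
| 56 | 308 | 252 | 0 | 56 (100%) |

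The documents do not report delays, so the table is a range, not an estimate. Late injections 1 to 4 followed by an on-time injection 5 lose nothing.

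**4. Which scheduled data are exposed.**
- The safety visit one week after injection 5 (Week 34, Protocol Appendix II: injection site evaluation, chemistry, liver function) falls at day 196 + d + 7. It stays inside day 252 while d ≤ 49, that is, up to a 7-week delay.
- For oral PrEP participants (Appendix III), the +8 visit has no history, chemistry or liver tests. These resume at +12, outside either window.
- For CAB LA continuers (Appendix IV), the +8 visit has chemistry and liver tests. Held on schedule, it falls at day 252 + d, outside the capped window for any d > 0 and on the edge of the uncapped one.
- Events reported between visits or at interim visits are also exposed.

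**5. Size for one late participant.** Assume a constant hazard and a risk P of a first Grade 2 or higher event over 252 days. The probability removed by the cap is [1 − (1 − P)^((252 + d)/252)] − P. For P of 0.3, 0.5, 0.7 and 0.9 the results span 0.3 to 0.4 points at d = 3, 1.2 to 1.9 at d = 14, 2.3 to 3.8 at d = 28, and 4.0 to 7.1 at d = 56. One participant 14 days late among nine changes the expected proportion by 1.2/9 to 1.9/9, about 0.13 to 0.21 points.

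**6. Size if it happens.** SAP 6.4 reports that accrual stopped at nine. One participant dropped from the numerator is 1/9 = 11.1 points if all nine were injected (more if fewer were), against 1/50 = 2 points at the planned size.

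**The case against.** **Week 41 may be a label.** Protocol Table 1.4 attaches Week 41 to 8 weeks after injection 5, and SAP 12.3 treats 36 weeks from first injection and 8 weeks after the Week 33 visit as interchangeable. On that reading nothing is cut. This shows that the text is ambiguous. It does not rescue the phrase, which would then be redundant for completers and still need a definition.

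**A cap can be defended.** The proportion with any event rises with time observed, and a cap at 36 weeks from the W5 visit holds late completers to the same total as on-time ones. That is true, and removing it gives them 36 weeks plus d. But equal follow-up does not explain the rule, because early stoppers already have shorter windows. For the same reason, the documents do not support the inference that late attenders are observed least overall; they lose time only after the last injection.

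**The events are not lost.** A reader might infer that they vanish from the trial. They do not: SAP 12.2, item 2, and SAP 12.3 still count them for completers. A secondary window that differs from the primary one is also no contradiction in itself. What stands is that the primary window is the shorter one for late completers, without a stated reason.

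**The worst cases are hypothetical.** A reader might suppose that successive two-week slips carry injection 5 to Week 41 and erase its follow-up. SAP 12.4 does not support this, since each target is fixed from the W5 visit and lateness does not move the later ones. How out-of-window participants are managed is in the SSP Manual, which is not among the documents. Injection site and laboratory checks one week after injection 5 survive all but very long delays.

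**Conclusion.** The point holds in a limited form. On the plain wording, with Week 41 as study time, SAP 8.1 cuts follow-up after a late last Step 2 injection by the days of delay, down to zero at 56 days. SAP 12.2, item 2, and SAP 12.3 for completers do not.

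The expected effect is small: at most 3 days if injection 5 is on time, and, under the constant-hazard assumption, about 0.2 points or less in the proportion for one participant two weeks late among nine. It runs one way, towards fewer events. The scheduled data mainly at risk are the +8 week chemistry and liver tests of CAB LA continuers.

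The 11.1-point figure should not be read as the effect of every missed event. The endpoint counts participants, so a late event changes the result only for someone with no Grade 2 or higher event since first injection. The figure also assumes that all nine enrolled were injected. The size of the real delays is unknown from the documents.

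**What to change.** In SAP 8.1, delete the Week 41 alternative together with its earlier-of rule, so that the window ends 8 weeks after the actual last Step 2 injection visit. Defining Week 41 as 8 weeks after the actual Week 33 injection visit would have the same effect for completers. Do not add a cut-off at the first Step 3 injection: SAP 12.3 has none, and an early +8 injection would shorten follow-up again. The primary window then matches SAP 12.3 for five-injection completers.

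In the same edit, reconcile SAP 8.1 with Protocol 7.7.1. The gap between 8 and 48 weeks after the last injection is larger than the one described here, and the cap widens it for late participants.

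Deleting the cap costs one phrase and needs no new data. The total window becomes longer by d days for late completers, and the Grade 2 or higher proportion may come out slightly less favourable.

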### **3.1 Inclusion Criteria**

Male adolescents who meet the following criteria are eligible for inclusion in this study:

- 3.1.1** Assigned male at birth (includes MSM, TGW, and gender non-conforming people)
- 3.1.2** At enrollment, aged below 18 years\*
- 3.1.3** At enrollment, body weight  $\geq 35$  kg (77 lbs.)\*
- 3.1.4** Willing to provide written informed assent/consent for the study and/or able to obtain written parental/guardian informed consent;
- *If not of legal age or otherwise not able to provide independent informed consent as determined by local law and consistent with site IRB/EC policies and procedures: Parent or legal guardian is willing and able to provide written informed consent for study participation and potential participant is willing and able to provide written assent for study participation.*
- *If of legal age or otherwise able to provide independent informed consent as determined by local law and consistent with site IRB/EC policies and procedures: Willing and able to provide written informed consent for study participation.*
- 3.1.5** Self-reported sexual activity with a male in the past 12 months;
- 3.1.6** In general, good health, as evidenced by the following laboratory values:
  - Non-reactive / negative HIV test results\*\*,
  - Absolute neutrophil count  $> 799$  cells/mm^3,  $\pm$
  - Platelet count  $\geq 100,000$  cells/mm^3,
  - Hemoglobin  $\geq 11$ g/dL,  $\pm$
  - Calculated creatinine clearance  $\geq 60$  mL/minute using modified Schwartz equation ( $\leq$  grade 2),
  - Alanine aminotransferase (ALT)  $< 2.0$  times the upper limit of normal (ULN) and total bilirubin (Tbili)  $\leq 2.5 \times$  ULN,
  - Hepatitis B virus (HBV) surface antigen (HBsAg) negative and accepts vaccination,
  - HCV Antibody negative.

**3.1.7** Willing to undergo all required study procedures

**3.1.8** If currently on PrEP from a non-study source, willing to stop said PrEP prior to enrollment and agree to switch to oral CAB for the lead-in period and CAB LA injections.

\*Please see [Section 1.7](#) for explanation.

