\*\*HIV-uninfected, based on HIV test results obtained at Screening and at the Enrollment visit. All HIV test results from the Screening visit must be obtained and must all be negative/non-reactive. This includes testing for acute HIV infection, which must be performed within 14 days of Enrollment. Individuals who have one or more reactive or positive HIV test result(s) will not be enrolled, even if subsequent confirmatory testing indicates that they are not HIV-infected (see SSP Manual).

‡ Participants below the cutoff may be considered for enrollment at the discretion of the PI and in consultation with the CMC if the PI can demonstrate that participant is in general good health despite being below the cutoff.

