### **7.7.3 AEs and Serious Adverse Events (SAEs)**

AEs will be tabulated using MedDRA preferred terms. The number and percentage of participants experiencing each specific AE (All AEs, Grade 2 or higher, and SAEs) will be tabulated by severity and by relationship to study product. For the calculations in these tables, each participant's AEs will be counted once as the maximum severity and relationship to study product. AEs leading to temporarily or permanently stopping drug will also be summarized. AEs will be summarized for those that are treatment emergent during LA dosing.

A listing of EAEs reported to the DAIDS RSC Safety Office will provide details of the events including severity, relationship to study product, time between onset and last injection, number of injections received, and a summary of the event.

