### **9.4 Pharmacology**

Blood samples will be collected throughout the study from all participants and assayed for plasma CAB concentrations. PK sample times include predose trough samples at W5, W9, W17, W25, and W33, (final concentration in injection phase) and 1-week post injection samples at W6, W10, W18, W26, W34. In addition, follow-up samples will be collected for 48 weeks([Appendix II](#) and [Appendix III or IV](#)) and at HIV confirmatory visit ([Appendix V](#)).

Plasma samples will be processed and frozen locally for subsequent shipment to the HPTN LC following procedures outlined in the SSP Manual. Pharmacology testing will be performed at the HPTN LC or at an outside laboratory designated by the HPTN LC. The primary pharmacologic assessments will be performed using assays that have been validated in accordance with regulatory requirements. Results will not be returned to the study participants or study sites.

Plasma and DBS samples will be processed and frozen locally for subsequent shipment to the HPTN LC following procedures outlined in the SSP Manual. Pharmacology testing will be performed at the HPTN LC or at an outside laboratory designated by the HPTN LC. The primary pharmacologic assessments will be performed using assays that have been validated and approved by the Clinical Pharmacology Quality Assurance (CPQA) Committee (reference assay validation report). Results will not be returned to the study participants or study sites. Plasma and DBS will be collected in Step 3 and if a study participant seroconverts for potential pharmacologic analysis of plasma TFV and DBS TFV-DP concentrations, respectively, to assess PrEP adherence.

Stored plasma may also be tested for the presence of other ARV drugs or other concomitant medications.

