2.2 Study Objectives and Endpoints

Primary objectives:

- To evaluate the safety, tolerability, and acceptability of CAB LA in healthy, HIV-uninfected male adolescents aged below 18 years.

Secondary objectives:

- To examine adherence to and timeliness of injections over time among adolescent participants provided CAB LA and information regarding its safety and efficacy.
- To examine patterns of sexual risk behavior over time among adolescent participants provided CAB LA and information regarding its safety and efficacy.
- To evaluate the safety of oral CAB during step 1 (oral phase) as well as all study products during the aggregate oral+injectable period for all enrolled participants. Additionally, we will include an intention to treat analysis for the primary safety endpoint.
- To characterize the pharmacokinetics of CAB LA
- Additional exploratory analyses will be done with the laboratory and clinical data, including resistance mutations

To achieve the primary and secondary objective, the planned primary and secondary endpoints are:

Primary endpoints:

Safety endpoint: Proportion of participants experiencing any Grade 2 or higher clinical adverse events (AEs) and laboratory abnormalities among participants who receive at least one injection of CAB LA. Laboratory abnormalities include grade 2 or above on tests include (CRF: Chemistry Panel, Fasting Lipid Test Results, Urinalysis, Hematology):

- Renal function: Creatinine, Creatinine clearance
- Hematology: Hemoglobin, Platelets, WBC, Neutrophils, Lymphocytes
- Liver function: Alkaline phosphatase, AST, ALT, Total bilirubin
- Electrolytes: Phosphorus, Calcium
- Other chemistries: CPK, Glucose, Amylase, Lipase,
- Urine test: Protein, Glucose
- Fasting Lipid Test Results: Total cholesterol, Triglycerides, LDL, HDL

Tolerability endpoint: Proportion of participants who receive at least 1 injection and who discontinue receiving injections prior to the full course of injections due to intolerance of injection, frequency of injections or burden of study procedures. Reasons for intolerance may include:

- Injection site reaction
- Participant refused further participation¹
- Participant lost to follow-up
- Participant is unwilling or unable to comply with required study procedures
- Participant refused further study product use
- Participant unable to adhere to visit schedule

¹Excluding cases in which reason for termination is unrelated to intolerance

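### The SAP's primary safety count opens at the first injection visit and has no treatment-emergent rule, so Grade 2+ findings that arose before any injection may be counted as injection-phase events

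*SAP*

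**What the plan says.** SAP 2.2 defines the primary safety endpoint as "Proportion of participants experiencing any Grade 2 or higher clinical adverse events (AEs) and laboratory abnormalities among participants who receive at least one injection". Its laboratory list includes "Renal function: Creatinine, Creatinine clearance" along with hematology, liver, chemistry, urine and lipid tests.

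SAP 8.1 sets the window "from the first injection visit to 8 weeks after the last Step 2 injection visit", or to Week 41 if that comes first. It limits laboratory abnormalities to those that were reported as AEs, and it refers to SAP 3.2 for aggregation. SAP 3.2 gives a maximum-severity rule and nothing on onset or baseline grade.

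The protocol differs on two points. Section 7.7.1 starts the primary safety count at the initial injection, not at the visit. Section 7.7.3, also under Primary Analyses, adds: "AEs will be summarized for those that are treatment emergent during LA dosing". SAP 3.2 repeats most of 7.7.3 but omits that sentence.

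The oral-phase count in SAP 12.2 runs from "enrollment to week 5 (oral phase (step 1), including interim visits".

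**The concern.** In a single-arm study no control group absorbs background findings, so the rule that decides which events belong to the injection phase has a direct effect on the result. As written, the SAP does not say whether a participant must have an event that begins after the injection, or whether a Grade 2 finding present within the window is enough. It also opens the window at a visit whose samples precede the dose. Two programmers following SAP 8.1 could report different primary proportions from the same data. Any error from this source attributes to the injection a finding that the injection cannot have caused. The same finding might also fall within the oral-phase count.

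**Working it through.** **1. Can a pre-injection finding reach the window?**

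- AEs of Grade 1 and higher are collected from Week 0 (Protocol 6.1), so Step 1 events are in the AE data.
- Grade 2 AEs other than ALT proceed to Step 2 (Protocol Table 5.1).
- CBC, chemistry, liver tests and urinalysis are all scheduled at Week 5 (Protocol Appendix II).
- Week 5 blood is drawn before dosing. Protocol 9.4 says "PK sample times include predose trough samples at W5", and Protocol 5.5 requires a same-day HIV result before the injection. I infer that the safety samples come from the same draw.
- Only safety results from previous visits must be reviewed before the injection (Protocol 5.5), so a new Grade 2 result in the Week 5 sample need not be known when the injection is given.
- The first injection counts as on time from 0 to 3 days after the Week 5 visit (SAP 2.2 and 12.4), so visit and injection can fall on different days.
- A completely missing AE start date is set to the date of first dose (SAP Appendix C). The SAP does not say whether this means oral CAB or the first injection, and the choice decides whether such an event falls in the window.

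The route is therefore open, though SAP 8.1 does not say that it must be taken.

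**2. The plan's own figure.** The only design figure for this proportion is the table of 95% CI half-widths at n = 50 (Protocol Table S1, SAP Table 2). The formula 1.96 × √(p(1−p)/50) gives 0.0832, 0.1109, 0.1270, 0.1358 and 0.1386 for p = 0.1 to 0.5. All match the table after rounding. A treatment-emergent rule changes who is counted, not these figures.

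**3. Effect of one participant.** SAP 6.4 gives a total accrual of nine; the number injected is not stated. If all nine were injected, one participant is 1/9 = 11.1 points. If eight were, it is 1/8 = 12.5 points. For example, 2/9 = 22.2% (exact 95% CI 2.8–60.0%) becomes 3/9 = 33.3% (7.5–70.1%).

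**4. Chance of a miscount.** Let p be the true proportion with a post-injection event and q the proportion with a counted pre-injection finding. The documents give neither, and I assume independence. Each participant counts once, so a pre-injection finding changes the result only if there is no true event. The per-person miscount probability, which is also the expected excess, is q(1−p). For nine injected, P(at least one miscounted) = 1 − (1 − q(1−p))^9.

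| p | q | q(1−p) | P(at least one of nine) |
|---|---|---|---|
| 0.2 | 0.05 | 0.040 | 1 − 0.960^9 = 0.31 |
| 0.2 | 0.10 | 0.080 | 1 − 0.920^9 = 0.53 |
| 0.5 | 0.05 | 0.025 | 1 − 0.975^9 = 0.20 |
| 0.5 | 0.10 | 0.050 | 1 − 0.950^9 = 0.37 |
| 0.8 | 0.05 | 0.010 | 1 − 0.990^9 = 0.09 |
| 0.8 | 0.10 | 0.020 | 1 − 0.980^9 = 0.17 |

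**The case against.** The strongest reply is that this is a wording gap in a plan that is not silent. Protocol 7.7.1 ties the count to events occurring from the initial injection, Protocol 7.7.3 names treatment-emergent events, and the AE start-date imputation in SAP Appendix C suggests assignment by onset date. SAP 8.1 also counts a laboratory value only if it was reported as an AE. This stands as a limit on the claim: pre-injection findings may count, but the documents do not show that they will. It does not remove the point, because the SAP changes the protocol's starting point and omits the treatment-emergent sentence.

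Four stronger readings are tempting and should not be drawn.

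- *Entry criteria guarantee carried-over Grade 2 events.* The creatinine clearance criterion, "using modified Schwartz equation", is annotated as allowing up to Grade 2, and for neutrophils and hemoglobin "Participants below the cutoff may be considered for enrollment at the discretion of the PI" with CMC consultation. But the documents give no grade limits for those two tests, and a stable entry value need not be recorded as an AE with onset in the window.
- *Week 5 results are counted in both phases.* Overlap is possible but not established. Week 5 belongs to the Step 2 schedule, and Protocol 7.8.2 defines the oral phase as Weeks 0 to 4. The two proportions are also never summed.
- *The findings cannot be due to the drug.* Participants have taken oral CAB for five weeks, and it is the same drug. Only the injection is ruled out as a cause.
- *The chance of a miscount is 37–61%.* That is 1 − (1−q)^9 for q = 5–10%, the chance that someone carries such a finding. It ignores that a carrier with a true event changes nothing.

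Carry-over is also bounded. Under Protocol Table 5.1, a repeat Week 4 ALT of Grade 2 or higher, related Grade 3 AEs, and Grade 4 AEs other than CPK keep a participant out of Step 2. Tabulation by relationship (SAP 3.2) and the change-from-baseline and shift summaries (SAP 9.2) help the reader, but SAP 9.2 uses the Safety population and neither alters the primary count.

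**Conclusion.** The point holds as a mis-set and incomplete counting rule, not as a demonstrated bias. SAP 8.1 departs from Protocol 7.7.1 on when the window opens, and SAP 8.1 and 3.2 neither carry over nor define the criterion in Protocol 7.7.3. Grade 2+ findings that predate any injection and are reported as AEs may enter the primary proportion, and the effect can only be upward.

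Each participant counted solely for such a finding adds about 11 points if all nine were injected, and more if fewer were. With assumed carry-over of 5–10% and a true event proportion of 0.5, the chance of at least one miscount is about 20–37%. Over true proportions of 0.2 to 0.8 it runs from 9% to 53%. These figures rest on assumed rates, on independence, and on nine injected; the requirement that a laboratory value be reported as an AE could lower them. The exact intervals at n = 9 are wide enough that one such shift lies well within sampling uncertainty. This is still a correction that should be made, because it costs little and the rule decides the primary result.

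**What to change.** - In SAP 8.1 and 12.3, count an AE if its onset is after the date and time of the first injection, or if it worsens above the last grade recorded before that injection. Use the last grade, not the highest: with the highest, a Grade 2 event that resolved in Step 1 and recurred at Grade 2 after injection would be lost. State a rule for events on the injection day with no recorded time.
- Define this as the meaning of treatment emergent, and cite Protocol 7.7.3.
- Treat predose Week 5 results as the pre-injection baseline and assign them to the oral phase only. Word SAP 12.2 accordingly and reconcile it with the Week 0 to 4 oral phase in Protocol 7.8.2.
- State in SAP Appendix C which first dose is meant when an AE start date is imputed.
- Apply the restriction to laboratory abnormalities reported as AEs in SAP 12.2 and 12.3 as well as in 8.1.
- List pre-existing Grade 2+ findings in a separate row beside the primary count.

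The cost is SAP wording and a baseline-grade flag in the analysis dataset; no new data are needed. The downside is that stable pre-existing abnormalities leave the primary count, which the separate row covers. Because the trial is open label and accrual has ended, the change should be dated, and if the data have already been reviewed, the count should be shown under both rules.
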